1. SPECIFIC AIMS

Metformin has emerged as a safe and modestly effective intervention for antipsychotic-associated weight gain, with several meta-analyses demonstrating mean weight loss of 3 kg in studies ranging from 12 to 24 weeks. Among FDA-approved weight loss agents, there have been few pharmacological options for people with schizophrenia because of the risk for psychotic exacerbation associated with sympathomimetic drugs which characterize a number of these agents. Lorcaserin is a 5-HT_{2C} agonist that has recently been approved for weight loss and represents a potentially important option for people with schizophrenia since it does not have sympathomimetic properties. The current study will examine the effectiveness of two novel weight loss approaches in schizophrenia – lorcaserin monotherapy and lorcaserin/metformin combination treatment – compared to placebo.

This study will enroll 110 overweight people with schizophrenia or schizoaffective disorder who have a BMI \geq 27 and are treated with one or a combination of two antipsychotic medications. Participants will be randomized to receive 52 weeks of lorcaserin/metformin combination treatment, lorcaserin monotherapy or placebo. All participants will receive a manualized behavioral intervention aimed at increasing physical activity and improving their diets.

Specific Aims:

1. Aim #1: Determine the efficacy of lorcaserin/metformin combination treatment and lorcaserin monotherapy on body weight in overweight people with schizophrenia.
 - a. Primary hypothesis:
Lorcaserin/metformin combination treatment will demonstrate greater weight loss compared to placebo.
 - b. Secondary hypothesis:
Lorcaserin monotherapy will demonstrate greater weight loss than placebo.
2. Aim #2: Determine the efficacy of lorcaserin/metformin and lorcaserin monotherapy compared to placebo for improving lipid and glucose metabolism.
 - a. Lorcaserin monotherapy and lorcaserin/metformin combination treatment will demonstrate greater improvement in markers of lipid and glucose metabolism compared to placebo.
3. Aim #3:
 - a. Determine the safety and tolerability of lorcaserin monotherapy and lorcaserin/metformin combination treatment using adverse event monitoring.

- b. Determine the effect of lorcaserin/metformin and lorcaserin monotherapy on the appetite regulating hormones. Peripheral leptin, total and acylated ghrelin, PYY3-36 and GLP-1 levels will be measured.

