3.2. SUBJECTS

Approximately 110 subjects will be recruited at four clinical sites (UNC Chapel Hill, Columbia University, Carolina Behavioral Care, and Augusta University) over a 30-month period, with the goal of randomizing 90 subjects. At UNC Hospitals in Chapel Hill, NC, ~650 outpatients with chronic psychotic disorders (80% of whom have schizophrenia or schizoaffective disorder) receive care in the Schizophrenia Treatment and Evaluation Program (STEP). A newly established UNC-STEP clinic in Raleigh, NC has an additional 500 schizophrenia patients. [name] runs a half-day clinic at both locations. He is also Research Director of the North Carolina Psychiatric Research Center, which is integrated into the STEP clinic infrastructure and thereby has full access to these patient populations. [name] will recruit subjects through the Lieber Schizophrenia Research Clinic at the New York State Psychiatric Institute (NYSPI). In addition he has access to ~1,100 patients with schizophrenia spectrum disorders in the Washington Heights Community Service Clinics, which serve the catchment area in New York City surrounding Columbia/NYSPI. Both of these sites successfully recruited for the METS study, which had similar inclusion/exclusion criteria.

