7. STATISTICAL ANALYSES

7.1. ANALYSIS POPULATIONS

Patients who are screened but not randomized will not be included in any efficacy or safety analyses of study data. However, the number of patients screened and reasons for any screen failures will be reported. SAEs occurring during the screening period will also be reported.

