interest will be the difference in weight change between the placebo and lorcaserin/metformin combination treatment. Although a mixed effects model will be used for data analysis, a one-way, three-group ANOVA on change scores was used as an approximation for estimating sample size, as use of a mixed model for such estimation would have required us to hypothesize a covariance structure, pattern of dropout, and a site effect. It is thus likely that our sample size estimates are conservative. In this model, for the primary contrast of placebo versus lorcaserin/metformin combination, to achieve power=0.85, with a two-tailed significance level of 0.05, will require 27 subjects per treatment group. A sample size of N=110 will be used in order to allow for ~25% dropouts.

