7.2.5. Missing Data

Data may become missing in several ways. Data may be sporadically missing because a subject failed to attend a scheduled visit and there are usually relatively few of these instances. If no more than 2 successive intermittent visits are missing, the data will be imputed. No more than 4 visits per subject will be imputed. Data may become missing when subjects drop out, and there is a danger that such missing data are informative, especially problematic when the proportion of the missing data is large (more than 20%). We will use sensitivity analyses to determine whether the amount of missing data is informative or non-informative, and the effect of such missing data on the results.

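### The ~25% dropout allowance in Section 7.2.1 needs about 108 randomised, but Section 3.2 plans to randomise 90, which leaves room for only 10% dropout

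*Combined protocol and SAP*

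**What the plan says.** Section 7.2.1 bases the sample size on a three-group ANOVA of change scores, used as a stand-in for the mixed model. It assumes weight losses of 1.5 kg on placebo and 6.5 kg on the combination, and an SD of change of 6 kg. For the primary contrast, "to achieve power=0.85" "with a two-tailed significance level of 0.05", the plan "will require 27 subjects per treatment group". It closes with: "A sample size of N=110 will be used in order to allow for ~25% dropouts".

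Two other sections give the size of the trial:

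- Section 1: "This study will enroll 110 overweight people with schizophrenia or schizoaffective disorder". It goes on to say that participants are randomised and does not mention 90.
- Section 3.2: about 110 are recruited, "with the goal of randomizing 90 subjects".

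Two passages bear on what counts as a dropout. Section 7.1 says: "Patients who are screened but not randomized will not be included in any efficacy or safety analyses of study data". It reports screen failures separately. Section 7.2.5 uses the term for loss during follow-up: "Data may become missing when subjects drop out".

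**The concern.** The figure of 110 does two jobs. In Section 7.2.1 it is the required number inflated for dropout, so it has to be the number randomised. In Section 3.2 it is the number recruited, of whom 20 are not expected to reach randomisation. Patients who are never randomised contribute nothing to the analysis and cannot serve as a reserve against later dropout.

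The number randomised and its power are basic design facts for the IRB, for the DSMB (which under Section 6.2 considers whether the study can test its hypotheses) and for readers. As written, sites that meet the Section 3.2 target would not deliver the sample that Section 7.2.1 relies on.

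**Working it through.** **Inputs.** From Section 7.2.1: difference 6.5 − 1.5 = 5 kg, SD 6 kg, two-sided alpha 0.05, power 0.85, 27 per arm, N = 110, dropout ~25%. From Section 3.2: about 110 recruited, 90 randomised. From Section 3.5.2: 1:1:1 allocation, so 90 randomised is 30 per arm.

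**Step 1: reproduce the plan's figure.** The two-arm contrast in a three-group ANOVA has noncentrality 5 / (6 × √(2/n)) and 3n − 3 degrees of freedom. At n = 27 the noncentrality is 5 / (6 × 0.2722) = 3.06 and power is 0.856. At n = 26 power is 0.843. So 27 per arm is right.

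**Step 2: inflate for dropout.** 3 × 27 = 81, and 81/0.75 = 108. The stated 110 agrees if it is the number randomised: the loss that still leaves 81 is 1 − 81/110 = 26.4%.

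**Step 3: apply the Section 3.2 target.** Loss before randomisation is 20/110 = 18.2%. The loss after randomisation that still leaves 81 is 1 − 81/90 = 10%.

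**Step 4: power on the plan's own approximation (completers only).**

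| Randomised | Dropout | Completers per arm | Power |
|---|---|---|---|
| 90 | 10% | 27 | 0.86 |
| 90 | 15% | 25.5 | 0.84 |
| 90 | 20% | 24 | 0.81 |
| 90 | 25% | 22.5 | 0.79 |
| 110 | 25% | 27.5 | 0.86 |

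At 25% dropout with 90 randomised, 90 × 0.75 = 67.5 complete, the noncentrality is 5 / (6 × √(2/22.5)) = 2.80, and power is 0.786. The type II error rises from about 14% (1 − 0.856) to about 21% (1 − 0.786).

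**Step 5: allow for the mixed model.** The documents give no covariance structure and no dropout pattern, so this step rests on assumptions. Power was taken from the generalised least squares variance of the week-52 contrast, with 17 post-baseline visits, a week-52 SD of 6 kg, covariance treated as known (slightly optimistic for an unstructured matrix) and 25% random monotone dropout placed early, uniformly or late. The covariances tried were compound symmetry and autoregressive with correlations 0.3 to 0.9, and a random walk with and without noise.

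- 90 randomised: 0.80 to 0.88, falling to about 0.79 if early dropout is spread over the first four visits.
- 110 randomised: 0.88 to 0.94, falling to about 0.865 under the same early pattern.

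These limits are illustrative. For 90 randomised the range lies on both sides of 0.85; for 110 it lies above 0.85 throughout.

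**The case against.** Only one figure in the document is explicitly called the number randomised, and that is 90. Section 7.2.1 does not say that its 110 are randomised. The numbers also chain together: 110 recruited, 90 randomised, 81 needed, and the total loss from 110 to 81 is 26.4%, close to the stated ~25%. On that reading Section 7.2.1 uses dropout loosely for all attrition from recruitment to week 52. This cannot be excluded, but it is unlikely given how Sections 7.1 and 7.2.5 keep the two kinds of loss apart. It also does not rescue the plan, because it leaves the same 10% for a 52-week trial.

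The second objection has more force. The 0.79 belongs to a completers-only analysis that will not be run. The primary model (Section 7.2) uses every visit and, under Section 7.1.2, everyone with at least one post-baseline weight. Section 7.2.1 itself calls its estimates likely conservative. It follows that a shortfall below 0.85 in the planned analysis is not proven. But the remark is not quantified, and the illustrative range for 90 does not settle it in the plan's favour. That range also assumes random dropout, whereas Section 3.5.5 makes a weight gain of more than 7 kg a discontinuation criterion, which ties loss to the outcome, and Section 7.2.5 itself warns of informative dropout.

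Finally, 10% is not a cliff: power is still 0.84 at 15% dropout and 0.81 at 20%. That is fair, and it makes the loss of power moderate.

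**Conclusion.** The concern holds. The calculation of 27 per arm is sound, and so is its inflation to about 108. What fails is the link to the trial that Section 3.2 describes: the ~25% allowance holds for about 110 randomised and not for 90, for which it is 10%. On the plan's own approximation, with a 5 kg difference, SD 6 kg and two-sided 0.05, randomising 90 with 25% dropout gives power of about 0.79 against the stated 0.85. The mixed model may or may not close that gap, and the documents do not contain what is needed to show it. The contradiction in trial size is certain from the text; the power shortfall is moderate and depends on how many drop out. The primary test and its significance level are not affected.

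**What to change.** State one number screened and one number randomised, and use them consistently in Sections 1, 3.2 and 7.2.1.

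If 90 is the number randomised, delete the statement that N = 110 allows for ~25% dropouts. In its place, say that 90 randomised (30 per arm) gives power of about 0.86 for the 5 kg difference if dropout is 10% or less, and about 0.79 if it is 25%, on the ANOVA approximation. In Section 1, make clear that 110 is the number screened or recruited. The cost is wording in three sections and a less favourable stated power; no extra patients are needed.

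If about 110 were meant to be randomised, the target of 90 in Section 3.2 has to be corrected and recruitment raised. That means up to 20 more randomised, and about 134 recruited if the yield of 90 from 110 carries over (110 × 110/90 = 134). That yield is an assumption with no support beyond the two targets. This is the costlier route and is not needed to remove the contradiction.

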7.2.2. Specific Aim #1

This aim will use weight measures to calculate means and standard deviations, along with their 95% confidence intervals, at each time point, along with correlations among time points.

7.2.3. Specific Aim #2

The response variable is the effect of LOR/MET, LOR monotherapy and placebo on fasting lipid levels (i.e., total cholesterol, HDL, LDL, triglycerides), fasting glucose, fasting insulin, and HgA1c. These variables are all numeric, and the analyses will be similar to those performed for weight.

7.2.4. Specific Aim #3

The response variable is the effect of lorcaserin/metformin, LOR monotherapy and placebo on appetite regulatory hormones, body fat distribution, food intake and energy expenditure. These variable are numeric and the analyses will be similar to those performed for weight

7.2.5. Missing Data

Data may become missing in several ways. Data may be sporadically missing because a subject failed to attend a scheduled visit and there are usually relatively few of these instances. If no more than 2 successive intermittent visits are missing, the data will be imputed. No more than 4 visits per subject will be imputed. Data may become missing when subjects drop out, and there is a danger that such missing data are informative, especially problematic when the proportion of the missing data is large (more than 20%). We will use sensitivity analyses to determine whether the amount of missing data is informative or non-informative, and the effect of such missing data on the results.

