7.2. STATISTICAL CONSIDERATIONS

The primary outcome is change in body weight at 52 weeks compared to baseline. The primary objective is to compare LOR/MET combination treatment with placebo. We will use a mixed model with treatment group, site and visit as factors, baseline as a quantitative covariate, and the treatment-by-visit and baseline-by-visit interaction terms. The unstructured (UN) variance/covariance matrix will be used for the analysis. The primary outcome will be a contrast examining the difference between treatment at the 52 week point for LOR/MET combination compared to placebo.

The secondary objective is to compare LOR treatment with placebo. This analysis will be performed similar to the comparison of LOR/MET combination treatment with placebo. This comparison will be declared significant if both, LOR/MET and LOR, comparisons are significant.

(We will also explore the data and calculate descriptive statistics and will use graphics, including box plots by treatment group, stem-and-leaf plots, normal probability plots, histograms and bar charts, and other graphics. In addition to the analyses above, we will perform sensitivity analyses using fasting glucose, insulin, appetite regulatory hormones, body fat distribution, smoking status, gender, and type of antipsychotic medication (low vs high liability for weight gain) as covariates in order to assess their impact on weight in this study.

We will follow the above plan for other key secondary weight and metabolic-related variables. These analyses are all exploratory. Adverse events will be tabulated by treatment arm.

7.2.1. Power and Sample Size Calculations:

Based on our preliminary data with metformin for weight loss and on the published literature with lorcaserin monotherapy (Smith et al., 2010; Fidler et al., 2011; O'Neil et al., 2012), the following weight loss is hypothesized: 1.5 kg for placebo, 4.5 kg for lorcaserin monotherapy, and 6.5 kg for lorcaserin/metformin combination. Based on the literature and on our METS trial, the standard deviation of the change scores is expected to be 6 kg. We felt that a 3 kg change would be a clinically important change, and hence, a difference between treatment groups of 3 kg (or more) in change from baseline would represent a clinically important effect. The primary contrast of

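### Section 7.2.5 imputes intermittent missing visits by an unnamed method, although the planned mixed model needs no imputation; week 52 is safe, but intermediate-visit and longitudinal lab results can be distorted.

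*Combined protocol and SAP*

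**What the plan says.** Section 7.2.5 sets the rule for sporadic gaps: "If no more than 2 successive intermittent visits are missing, the data will be imputed", and "No more than 4 visits per subject will be imputed". It does not say whether imputation is single or multiple, how its uncertainty enters the standard errors, which variables it covers, or what happens to a subject above the limits. No imputation is stated for dropout. There the plan is "We will use sensitivity analyses to determine whether the amount of missing data is informative or non-informative".

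Section 7.2 gives the analysis: "We will use a mixed model with treatment group, site and visit as factors, baseline as a quantitative covariate", with treatment-by-visit and baseline-by-visit terms. It adds "The unstructured (UN) variance/covariance matrix will be used for the analysis". The primary result is the week-52 contrast between the combination and placebo.

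Section 7.2.2 adds means and standard deviations of weight, "along with their 95% confidence intervals, at each time point, along with correlations among time points". Section 7.2.3 says of the metabolic variables that "the analyses will be similar to those performed for weight", and section 7.2.4 says much the same for appetite hormones, body fat, food intake and energy expenditure. Section 7.2 labels the secondary weight and metabolic analyses exploratory.

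**The concern.** A likelihood-based mixed model with visit as a factor and unstructured covariance takes each subject's observed visits as they are. If values are missing at random given the observed data, it gives valid estimates and standard errors with the gaps left open. Imputing first therefore cannot improve validity. At best it changes nothing.

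At worst it does harm in one of two ways. A fill that ignores its own uncertainty, such as an arm mean or a regression prediction, makes standard errors too small. A fill that borrows an earlier value pulls the estimated effect toward the earlier visit. Because no method is named, the choice between these outcomes is still open when the data are in hand.

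**Working it through.** **1. The plan's own figure.** Section 7.2.1 assumes losses of 6.5 and 1.5 kg (difference 5 kg), SD 6 kg, two-sided 0.05 and power 0.85. The normal approximation gives n = 2(1.96 + 1.036)² × 6²/5² ≈ 25.9, so 26 per group. The noncentral t gives 27 (power 0.852, or 0.856 with the three-group error degrees of freedom), which is the plan's number. For 25% dropout, 81/0.75 = 108, close to the stated 110. None of this depends on imputation.

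**2. What the rule can reach.**
- Weight (section 3.9.3.3) is taken at Visits 1 to 17. Visit 17 (week 52) has no later visit, so only Visits 1 to 16 can be intermittent gaps.
- Four-visit patterns: C(16,4) = 1,820. Of these, 13 have a run of four and 156 a run of exactly three, leaving 1,651 allowed. The ceiling is 4/17 = 23.5% of weights.
- Lipids, glucose and HbA1c are measured on treatment at Visits 7, 10 and 17 (sections 3.8.9, 3.8.12, 3.8.19; Appendices 1 and 2). Visits 7 and 10 are not adjacent, so both can be filled: 2 of 3.
- Insulin and appetite hormones are measured at Visits 10 and 17: 1 of 2.

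**3. How often.** Assume visits are missed independently with probability 5% to 15%.
- Visits 7 and 10 both missed: 0.05² = 0.25% to 0.15² = 2.25% of subjects.
- Four or more of 16 weights missed (binomial, dropout ignored): 0.7% at 5% and 21% at 15%.
- The 1-of-2 case arises whenever Visit 10 is missed, so in 5% to 15%.

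The weight ceiling is therefore rare if gaps are as few as section 7.2.5 expects, but not at 15%.

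**4. Week 24, arm-mean fill.** Let a fraction m be filled with the arm mean (baseline adjustment ignored).
- Reported SE = √(2(1 − m)σ²/n).
- True SE = √(2σ²/((1 − m)n)).
- Ratio = 1 − m, so type I error = 2[1 − Φ(1.96(1 − m))].
- m = 0.10: 2[1 − Φ(1.764)] = 7.8%. m = 0.20: 2[1 − Φ(1.568)] = 11.7%.

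Simulation agrees (assumptions: 30 per arm, correlation 0.6, 10% and 20% of week-12 and week-24 values missing at random, 4,000 null runs):

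| Method | Type I error, 10% missing | 20% missing |
|---|---|---|
| No imputation | 5.0% | 4.6% |
| Arm mean | 7.7% | 11.6% |
| Regression | 7.5% | 10.3% |

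**5. Week 24, last value carried forward.** Let r be the week-12 effect as a share of the week-24 effect, with baseline carried when week 12 is also missing. Shrinkage = m[1 − r(1 − m)]. With r = 0.6 (assumption) this is 0.10 × 0.46 = 4.6% and 0.20 × 0.52 = 10.4%. Simulation gave 6 to 11%, with type I error near 5%. Linear interpolation shrank the effect by 1 to 6%, depending on the assumed week-12 effect, and held its error rate.

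**6. Full 17-visit unstructured model.** Assumptions: 37 per arm, SD 6 kg at week 52, 25% dropout, 5% or 15% missed per visit, 80 runs per scenario.
- Week 52: every fill gave an estimate within about 0.02 kg of no imputation and an SE within about 1%.
- Week 24, 15% missed, visit-mean fill: model SE 0.931 against empirical 1.149, 19% low. Without imputation the pair was 1.016 and 1.106, 8% low. With 80 runs an empirical SE carries about 1/√158 = 8% Monte Carlo error, so the paired comparison is safer: visit-mean fill cut the reported SE by 8% (0.931/1.016) while the actual spread rose by 4% (1.149/1.106).
- Gaps for last value carried forward (3%) and interpolation (5%) are within noise.

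**The case against.** The strongest reply is that the harm is inferred and lies away from anything confirmatory.

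- A reader might infer that the filled values will be analysed as if measured. The text does not say so. Limits on eligible gaps fit multiple imputation as well as single, and properly combined multiple imputation would not understate the standard errors. This stands: what is documented is an unnecessary step with no method, not a commitment to single imputation.
- A reader might infer that the primary result is at risk. It is not, since week 52 is never filled. Section 7.2 defines only a week-52 contrast, and if the lab variables are tested there too, they are nearly safe. A simulation on the week 12, 24 and 52 schedule (30 per arm, correlation 0.6, 25% dropout, 1,500 runs) gave week-52 type I error of 4.6 to 6.1% across all methods, with Monte Carlo error of about 0.6 points. This also stands. However, section 3.3.1 describes a longitudinal analysis across the year and names no test visit, and section 7.2.2 reports every visit.
- A reader might infer that most of a subject's lab values will be imputed. Two of three is a rare ceiling for lipids, glucose and HbA1c only. For insulin and each hormone it is half. That the rule covers labs at all is read across from the statements that those analyses resemble the weight analysis.
- Interpolation, which suits short gaps with a later observation, would do little damage. True, but the plan does not choose it.

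What survives is narrower: a stated step with no benefit that, under common ways of carrying it out, distorts intermediate-visit results.

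**Conclusion.** The point holds as a minor one. The imputation rule is redundant next to the section 7.2 model, and its method and variance handling are unspecified. The primary contrast and the sample size are not in question.

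If single imputation is used, the exposed results are the intermediate-visit estimates, the visit-wise intervals and correlations (if computed on the filled data), and the exploratory longitudinal lab and hormone analyses. The size rests on assumptions that the documents do not supply (10 to 20% missing, correlation 0.6, about 30 per arm). On those, a nominal 5% week-24 test runs at about 7 to 12% under arm-mean or regression fill, the effect is understated by about 6 to 11% when the last value is carried forward, and interpolation costs little. With properly combined multiple imputation the standard-error problem would not arise, but the step would still be unnecessary.

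**What to change.** Delete the two imputation sentences in section 7.2.5. In their place, state that intermittent missing values stay missing and are handled by the likelihood of the section 7.2 mixed model under missing at random, for weight and for the Aim 2 and Aim 3 variables analysed in the same way. If imputation is kept, make it multiple imputation, name the imputation model and the variables covered, combine the variance properly, and use it only as a sensitivity analysis.

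The cost is a change of wording. There is less work than under the current plan, no new data are needed, and 27 per group and N = 110 do not change.
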